4.8.2 Baseline Visit - Initial treatment (Day 1)

The baseline visit can be performed in direct connection with the screening visit or at the latest 21 days after the screening visit.

If the screening and baseline visits are separated, the inclusion and exclusion criteria will be re-checked and if any changes have occurred in the health status, concomitant medication and procedures will be assessed before the subject can be included in the study.

Further, vital signs will be assessed, standardized pre-treatment photograph will be taken as described in Section 7.5, and a pregnancy test (U-HCG) will be performed in women of childbearing potential. Before treatment, the blinded evaluator will make a live assessment to evaluate the wrinkle severity on WSRS to obtain a baseline value.

- Interview for medical history and concurrent diseases
- Interview for concomitant medications and treatments
- Vital signs (pulse rate, blood pressure, respiratory rate, and axillary temperature)

 GALDERMA	Title 43CH1508 Clinical Study Protocol	Doc id MA-29708
--	---	----------------------------------

Effective date: 2017-07-05 06:37

Effective date:

Effective

Version: 5.0

- Perform urine pregnancy test for all women of childbearing potential (if ≥ 2 weeks since the pregnancy test performed at the screening visit)
- Assess WSRS to obtain a baseline value (by blinded evaluator)
- Confirm eligibility criteria

[figure not shown]
For each eligible subject, one NLF will be randomly assigned to treatment with Restylane Defyne (with lidocaine) and the opposite NLF to treatment with Restylane (without lidocaine). Treatment will be administered according to the instructions in Section 6.6. Any device deficiencies or AEs since last visit, during or after the treatment will be reported. **CCI**

CCI

[figure not shown]
- Randomize the subject and arrange for blinding of the subject
- Obtain a pre-treatment photograph (baseline)
- Perform treatment in the right NLF according to randomization (Section 6.6)

CCI

- Perform treatment in the left NLF according to randomization (Section 6.6)

CCI

- Interview for AE since last visit and evaluate the subject for post-treatment AEs
- Evaluate device deficiencies

4.8.3 Week 4 follow-up after initial treatment (Day 29 ± 3 days) / Optional touch-up

A follow-up visit will take place 4 weeks ($D29 \pm 3$ days) after the initial treatment. An optional touch-up treatment may be performed if optimal aesthetic improvement was not obtained.

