6.6.2.2 Touch-up treatment

A touch-up treatment may be performed four weeks after the initial treatment if optimal correction has not been achieved, as assessed by the blinded valuator. If a touch-up is performed it should preferably be performed in both NLFs. For subsequent touch-up treatment, it is recommended not to use more than 0.5 mL for each NLF. It is of outmost importance that the subject receives the same product as received at the initial treatment in respective NLF.

Topical or local anesthetic or other pain-relieving medication, including ice, may be used before and after touch-up treatment.

Touch-up will not be performed without the subject's verbal consent, if there are ongoing treatment-related AEs, or if optimal aesthetic improvement is already achieved.

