8.4.8 Anticipated adverse events

After the injection some common injection-related reactions might occur with both products. These reactions include bruising, erythema, swelling, pain, tenderness and itching at the injections site. Typically these reactions start on the day of treatment and resolve spontaneous within a few days after injection. This is in line with what has been observed in the Chinese clinical study for Restylane and is also consistent with international clinical study results for Restylane and Restylane Defyne.

Refer to the Restylane Defyne IB and EU IFU ([Appendix 2](#)) as well as the Restylane China IFU ([Appendix 3](#)).

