1.6 Safety Endpoints

Safety endpoints include:

- (i) **Incidence, intensity, duration and time to onset of related treatment emergent AEs collected during the whole study**

CCI

2 Statistical Methods

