Concomitant medication taken due to an AE will be summarized by ATC code (along with an ATC text description) and in total using number and percentage of subjects and number of medications, and by MedDRA coded AE and whether the AE is related or not (Table 6-5).

 GALDERMA	Title SAP, 43CH1508, Restylane Defyne NLF	Doc id MA-31549
--	---	---------------------------

Concomitant procedures/treatments will be presented using number and percentage of subjects (Table 6-6), as well as by reason and in total using number and percentage of subjects and number of procedures/treatments (Table 6-7).

2.3.5 *Extent of exposure*

Injection volume (mL), for each treatment visit and in total will be presented by treatment (Table 7-1) using number of subjects, mean, standard deviation, minimum, median, and maximum values. The same summary will also be generated by site and in total (Table 7-4). Within-subject difference (Restylane minus Restylane Defyne) of injected volume (mL) will be presented by treatment visit and in total by number of subjects, mean, standard deviation, minimum, median, and maximum values (Table 7-2).

Injection time (minutes) for each treatment and within-subject difference (Restylane minus Restylane Defyne) in injection time (minutes) will be summarized using number of subjects, mean, standard deviation, minimum, median, and maximum values (Table 7-3).

Optional touch-up treatment eligibility evaluation (No/Yes) after initial treatment will be summarized by 3 eligibility questions using number and percentage of subjects (Table 7-5). In addition, number and percentage of subjects receiving touch-up treatment will be presented.

Number and percentage of subjects in each category and in total for injection method (Table 7-6), injection depth (Table 7-7), topical/local anesthesia used (Table 7-8), post-treatment care (Table 7-9), technical problems/device deficiencies (Table 7-10), deviations from the treatment procedure (Table 7-11), and directly observed AEs associated with the injection (Table 7-12) will be presented by treatment visit and treatment.

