2.5 Safety Analysis

All safety variables will be summarized descriptively based on the safety population.

CCI

2.5.2 *Adverse events*

All AEs will be coded according to MedDRA. Treatment emergent adverse events (TEAEs) will be summarized by System Organ Class (SOC) and Preferred Term (PT). The same summaries will be generated for treatment emergent related AEs, severe AEs, AEs leading to discontinuation, and serious AEs (SAEs). An overall summary of number and percentage of subjects with TEAEs reported in total, no TEAEs reported, related and unrelated TEAEs, and the number of events will be compiled (Table 9-5).

For related TEAEs, intensity of the AE will be summarized (Table 9-6). The number of days to onset (Table 9-8) and duration of event (Table 9-7) will be summarized by SOC and PT using number of events, mean, standard deviation, minimum, median, and maximum statistics. Action taken due to a related TEAE will be summarized by SOC, PT, and treatment (Table 9-9) using number of events.

Number and percentage of subjects with unrelated TEAEs and number of events will be presented by SOC, PT and intensity (Table 9-10).

Time to onset of a TEAE will be derived as the start date minus Day 1. If the start date is missing, it will be assumed that the AE started on Day 1.

Duration of a TEAE will be derived as the stop date minus the start date +1. If the start date is missing, it will be assumed that the AE started on Day 1. Missing stop date will not be imputed and therefore no duration will be calculated in these cases. Instead, the number of TEAEs that were ongoing at the end of the study will be given.

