1) List technical problems (device deficiencies) for the initial treatment here.

2) List technical problems (device deficiencies) for the touch-up treatment here.

 GALDERMA	Title SAP, 43CH1508, Restylane Defyne NLF	Doc id MA-31549
---	--	--------------------

Table 7-11: Deviations from the treatment procedure as described in the study protocol by treatment visit and treatment, FAS

Any deviations from the treatment procedure	Initial treatment ¹⁾				Optional touch-up treatment ²⁾			
	Restylane Defyne		Restylane		Restylane Defyne		Restylane	
	n	%	n	%	n	%	n	%
No								
Yes								
Total (N)								

% = $n/N * 100$

1) List deviations from the treatment procedure for the initial treatment here.

2) List deviations from the treatment procedure for the touch-up treatment here.

Table 7-12: Directly observed AEs or clinical complications associated with the injection by treatment visit and treatment, FAS

AEs associated with the injection	Initial treatment ¹⁾				Optional touch-up treatment ²⁾			
	Restylane Defyne		Restylane		Restylane Defyne		Restylane	
	n	%	n	%	n	%	n	%
No								
Yes								
Total (N)								

% = $n/N * 100$

1) List directly observed AEs associated with the injection for the initial treatment here.

2) List directly observed AEs associated with the injection for the touch-up treatment here.

8 Appendix E: Efficacy Evaluation

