9.3.2 Related TEAEs

Table 9-6: Related TEAEs by MedDRA System Organ Class, Preferred Term, and intensity, Safety population

Primary System Organ Class Preferred Term	Restylane Defyne									Restylane									Total					
	Events	Subjects	Intensity						Events	Subjects	Intensity						Events	Subjects						
			Mild		Moderate		Severe				Mild		Moderate		Severe									
	n	n	%	n	%	n	%	n	%	n	n	%	n	%	n	%	n	n	%	n	%			
SOC																								
PT																								
PT																								
...																								
SOC																								
PT																								
PT																								
...																								
All¹⁾																								

% = n / number of subjects in Safety population (N = xxx) * 100

1) A single subject may have reported several related TEAEs.

 GALDERMA	Title SAP, 43CH1508, Restylane Defyne NLF	Doc id MA-31549
--	--	--------------------

Table 9-7: Duration (number of days days) of related TEAEs by MedDRA System Organ Class and Preferred Term, Safety population

Primary System Organ Class Preferred Term	Restylane Defyne						Restylane					
	Events n	Mean	SD	Min	Median	Max	n	Mean	SD	Min	Median	Max
SOC												
PT												
PT												
...												
SOC												
PT												
PT												
...												
All												

If applicable, list TEAEs ongoing at study end here, alternatively create a summary table.

 GALDERMA	Title SAP, 43CH1508, Restylane Defyne NLF	Doc id MA-31549
--	--	--------------------

Table 9-8: Time to onset (number of days) from treatment for related TEAEs by MedDRA System Organ Class and Preferred Term, Safety population

Primary System Organ Class Preferred Term	Restylane Defyne						Restylane					
	Events n	Mean	SD	Min	Median	Max	n	Mean	SD	Min	Median	Max
SOC												
PT												
PT												
...												
SOC												
PT												
PT												
...												
All												

Any extra comments here...

 GALDERMA	Title SAP, 43CH1508, Restylane Defyne NLF	Doc id MA-31549
--	--	--------------------

Table 9-9: Action taken due to related TEAEs by MedDRA System Organ Class and Preferred Term, Safety population

Primary System Organ Class Preferred Term	Action Taken							
	Restylane Defyne				Restylane			
	None	Medication treatment	Non-pharmacological treatment or other procedures/tests	Subject withdrawn	None	Medication treatment	Non-pharmacological treatment or other procedures/tests	Subject withdrawn
SOC								

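### Time to onset is counted from Day 1 even after a touch-up, so a same-day touch-up reaction enters SAP Table 9-8 at 25 to 31 days

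*SAP*

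**What the plan says.** SAP 1.6 lists as a safety endpoint "Incidence, intensity, duration and time to onset of related treatment emergent AEs collected during the whole study". SAP 2.5.2 gives one derivation for the onset component: "Time to onset of a TEAE will be derived as the start date minus Day 1". The result goes to Table 9-8, headed "Time to onset (number of days) from treatment for related TEAEs by MedDRA System Organ Class and Preferred Term, Safety population". That table has columns for the two products but no split by treatment visit.

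Day 1 is the initial treatment (Protocol 4.1). A second injection is possible at the visit described as "Week 4 follow-up after initial treatment (Day 29 ± 3 days) / Optional touch-up". Protocol 4.7, Table 1, footnote c counts the touch-up as a treatment: the last treatment can be either injection, and the Month 3 to Month 12 visits are timed from it. On the folds, Protocol 6.6.2.2 says: "If a touch-up is performed it should preferably be performed in both NLFs". On the expected timing of injection reactions, Protocol 8.4.8 says: "Typically these reactions start on the day of treatment and resolve spontaneous within a few days after injection".

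Protocol 10.5 asks for the number of days to onset of related AEs but names no origin. No visible text in either document re-anchors onset to the touch-up date.

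**The concern.** The visit schedule restarts its clock at the touch-up and the onset derivation does not. After a touch-up, the value in Table 9-8 is no longer the time since the injection that most plausibly caused the event.

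This matters because early and late reactions have different clinical meanings. The instructions for use of both products (Protocol Appendices 2 and 3) report implant-site inflammation beginning either soon after injection or up to several weeks later. An onset summary should help a reader separate the two. With Day 1 as the only origin, a row with a maximum of 28 days could mean an ordinary same-day reaction to touch-up or a delayed reaction to the first injection.

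**Working it through.** **Inputs from the documents.** Onset = AE start date − Day 1 (SAP 2.5.2). Touch-up falls on Day 26 to Day 32 (Protocol 4.8.3). Injection reactions typically start on the day of treatment (Protocol 8.4.8). The plan states no figure to reproduce.

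**Assumed inputs.** Touch-up share, event counts and reaction rates are illustrative, because the documents give none. Each example describes a single row of Table 9-8, which reports by SOC and PT.

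**1. Value recorded for a same-day touch-up reaction.**
- Touch-up on Day 26: 26 − 1 = 25 days.
- Touch-up on Day 29: 29 − 1 = 28 days.
- Touch-up on Day 32: 32 − 1 = 31 days.

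Counted from the touch-up itself, each value is 0.

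**2. Effect on a row with no late events.** Assume 30 same-day reactions to the initial injection and 6 same-day reactions to touch-up. The mean under the SAP rule is 6d/36.

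| Touch-up day | d | Mean | SD | Median | Max |
|---|---|---|---|---|---|
| 26 | 25 | 4.2 | 9.4 | 0 | 25 |
| 29 | 28 | 4.7 | 10.6 | 0 | 28 |
| 32 | 31 | 5.2 | 11.7 | 0 | 31 |

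Counted from the latest injection, every entry is 0.

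**3. Two different safety pictures, one row.** Keep the 30 same-day initial reactions and let the other six values be 28 days. They are either (a) same-day reactions to a Day 29 touch-up or (b) reactions delayed 28 days in folds that had no touch-up. Under the SAP rule both give n 36, mean 4.7, SD 10.6, median 0, maximum 28. Counted from the latest injection, (a) gives mean 0 and maximum 0, while (b) gives mean 4.7 and maximum 28. The two cases coincide for any counts, since the derivation assigns them the same values.

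**4. Which statistics must move.** AEs are collected to Month 12, so add three related events with onset at 180 days to the 36 in step 2, with touch-up at Day 29.
- Six touch-up events counted as 0: mean = 540/39 = 13.8, SD 48.6, maximum 180.
- Six touch-up events counted as 28: mean = (540 + 168)/39 = 18.2, SD 48.4, maximum 180.

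The mean rises, the SD falls slightly and the maximum does not change. Only the rise in the mean is certain.

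**5. Median.** Let t be the share of folds touched up. If initial and touch-up injections have equal same-day reaction rates, touch-up events make up t/(1 + t) of the total: 9%, 17% and 23% for t = 0.1, 0.2 and 0.3. That is below half for any t below 1, so the median stays at 0.

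**6. Difference between products.** On the assumptions of step 5, with touch-up at Day 29, the mean for a product is 28t/(1 + t). Assume 35 of 175 subjects are touched up.
- All bilateral: t = 35/175 = 0.20 for both products, so both means are 5.6/1.20 = 4.7 and the difference is 0.
- 25% one-sided, all on the same product: t = 0.20 against 26.25/175 = 0.15, giving 4.7 against 3.7, a difference of 1.0 day.
- 50% one-sided, all on the same product: t = 0.20 against 17.5/175 = 0.10, giving 4.7 against 2.5, a difference of 2.1 days.

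If touch-up produces reactions at a fraction r of the initial rate, the mean is 28tr/(1 + tr). With t = 0.20 this is 2.8/1.1 = 2.5 days for r = 0.5 and 1.4/1.05 = 1.3 days for r = 0.25.

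**The case against.** The best defence is that start date minus Day 1 is an explicit, reproducible convention applied equally to both products. The Table 9-8 heading can be read as meaning the initial treatment, and Protocol 10.5 fixes no origin, so no protocol requirement is breached. All of that is fair, and relabelling would cure the mismatch between heading and rule. It would not separate the two cases in step 3 of the working.

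Table 7-12 gives partial cover. SAP 2.3.5 says "directly observed AEs associated with the injection (Table 7-12) will be presented by treatment visit and treatment", and the shell in Appendix D is titled "Directly observed AEs or clinical complications associated with the injection by treatment visit and treatment, FAS". It is a Yes/No count with footnoted events and no onset statistic, and a reaction that starts after the subject has left the clinic is not directly observed.

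The effect may also be small. The recommended touch-up maximum is 0.5 mL per fold against 1.5 mL initially, and Protocol 2.7 ties most events to injected volume and technique. Touch-up is limited to consenting subjects who have a fold without a one-grade improvement and no ongoing treatment-related AE. A reader with AE start dates and injection dates could separate the cases by hand.

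Two stronger readings are tempting. A reader might infer that the mean, SD and maximum are all inflated. Step 4 shows that this does not follow once later-onset related events occur. A reader might also infer that the comparison between products is biased. That needs touch-ups or reaction rates to be unbalanced between folds, and nothing in the documents shows that they will be.

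**Conclusion.** The point holds as a minor defect in descriptive safety reporting. The 25 to 31 day value for a same-day touch-up reaction follows directly from the stated rule and visit window. So does its confusion in Table 9-8 with a reaction delayed about four weeks. The mean onset is raised whenever related reactions follow a touch-up. The SD and maximum may rise, and the median will usually not move.

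The overall size is unknown. Means of roughly 1 to 5 days in the examples without late events rest on assumed counts, touch-up shares and reaction rates. The primary non-inferiority analysis and AE incidence are unaffected. Much of the safety material is redacted, so whether another table separates these events cannot be judged.

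**What to change.** In SAP 2.5.2, derive time to onset for Table 9-8 as AE start date minus the date of the latest injection of the affected fold on or before that start date. If no fold is recorded, which can happen because Protocol 8.4.3 asks for affected area only where applicable, use the subject's latest injection in either fold.

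Keep days since Day 1, labelled as from initial treatment, as a second line in Table 9-8 or in the AE listing. Both origins are needed, because the new one alone can make a delayed reaction to the first injection look early. A reaction starting on Day 31 after a Day 29 touch-up is 31 − 29 = 2 days from the latest injection and 31 − 1 = 30 days from Day 1. The existing rule for missing start dates can stay as it is.

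The cost is one changed derivation, its SAP wording, and one table line or listing column. Injection dates (Protocol 6.6.5) and AE start dates (Protocol 8.4.3) are already in the eCRF, so no new data are needed. The table becomes slightly longer, and for events soon after a touch-up neither origin alone shows which injection was responsible.

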8.4.6 Follow-up of unresolved events after termination of the study

All serious as well as non-serious AEs with a causal relationship to the study product or treatment procedure and ongoing at study end, shall be followed up after the subject's participation in the study is over. Such events shall be followed-up after the last study visit until resolved, assessed as chronic or stable, or for at least 3 months. Final outcome after the end of the study shall be reported on the AE follow up module in the eCRF.

	Title 43CH1508 Clinical Study Protocol	Doc id MA-29708
--	---	----------------------------------

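### Duration of related adverse events is summarised only over events with a stop date, so its mean and maximum can be understated if any are unresolved

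*SAP*

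**What the plan says.** SAP 1.6 names the endpoint: "Incidence, intensity, duration and time to onset of related treatment emergent AEs collected during the whole study". SAP 2.5.2 defines it: "Duration of a TEAE will be derived as the stop date minus the start date +1". Durations "will be summarized by SOC and PT using number of events, mean, standard deviation, minimum, median, and maximum statistics", shown per product in Table 9-7. Protocol 10.5 specifies the same statistics.

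For events without an end date, SAP 2.5.2 says: "Missing stop date will not be imputed and therefore no duration will be calculated in these cases". It continues: "Instead, the number of TEAEs that were ongoing at the end of the study will be given". The note under Table 9-7 (SAP 9.3.2) adds: "If applicable, list TEAEs ongoing at study end here, alternatively create a summary table".

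Protocol 8.4.6 covers related events still open when the subject leaves the study: "Such events shall be followed-up after the last study visit until resolved, assessed as chronic or stable, or for at least 3 months". The final outcome goes into an AE follow-up module of the eCRF. Neither document says whether a stop date recorded there enters Table 9-7.

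**The concern.** For a given start date, a longer event is more likely to be unresolved at last contact. Whether an event enters Table 9-7 therefore depends on the quantity the table measures.

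Most injection reactions are expected to settle within days (Protocol 8.4.8). Protocol 2.7 also names palpable lumps as a risk, and both Instructions for Use list mass, induration and nodules. If such events persist to the end of observation, they are the ones left out. A product with more persistent events could then show much the same mean and maximum as the other. Safety is only described, not tested, and the study is meant to support registration (Protocol 2.5), so these figures are the duration evidence a reader will have.

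**Working it through.** **1. Which events count.** Duration = stop date − start date + 1. With no stop date there is no duration, so the event cannot contribute to the mean, SD, median or maximum. The reported maximum cannot exceed the time observed. The rule for missing start dates ("If the start date is missing, it will be assumed that the AE started on Day 1") can only lengthen a duration, and it does nothing for an event without a stop date.

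**2. No plan figure to reproduce.** Neither document gives an expected duration or an expected number of ongoing events. The rest is illustration on stated assumptions.

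**3. Lower bound on the mean.** Let *m* be the mean over events with a stop date, *f* the share ongoing, and *c* their length observed so far. Counting ongoing events at *c* gives (1 − *f*) × *m* + *f* × *c*. This is a lower bound, because those events have not ended. Assume *m* = 5 days, in line with the 3 to 7 days in the Restylane China Instructions for Use (Protocol Appendix 3).

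| *f* | Table 9-7 mean | Bound, *c* = 30 days | Bound, *c* = 365 days |
|---|---|---|---|
| 0 | 5 | 5 | 5 |
| 1% | 5 | 4.95 + 0.30 = 5.25 | 4.95 + 3.65 = 8.6 |
| 5% | 5 | 4.75 + 1.50 = 6.25 | 4.75 + 18.25 = 23.0 |
| 10% | 5 | 4.50 + 3.00 = 7.5 | 4.50 + 36.50 = 41.0 |

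**4. Simulation with late-starting events.** 400,000 events were simulated, with 80% starting on Day 1 and 20% uniformly over 365 days. Durations are exponential with mean 5 days, except for a share *q* with mean 180 days. An event is excluded if it ends after the cut-off: Day 365, or Day 455 if three months of follow-up supply stop dates. All these rates are assumptions.

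| *q* | Excluded at Day 365 | True mean | Mean of included, Day 365 | Mean of included, Day 455 | Median, true / included at Day 365 | Excluded at Day 365 with true length under 30 days |
|---|---|---|---|---|---|---|
| 0 | 0.29% | 5.51 | 5.50 | 5.51 | 4 / 4 | 99% |
| 1% | 0.51% | 7.26 | 6.43 | 6.67 | 4 / 4 | 62% |
| 5% | 1.24% | 14.30 | 10.27 | 11.35 | 4 / 4 | 24% |
| 10% | 2.21% | 23.23 | 15.03 | 17.21 | 5 / 4 | 13% |

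The shortfall in the mean at Day 365 is:
- *q* = 1%: 1 − 6.43/7.26 = 11%
- *q* = 5%: 1 − 10.27/14.30 = 28%
- *q* = 10%: 1 − 15.03/23.23 = 35%

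At Day 455 the corresponding figures are 8%, 21% and 26%. Using the follow-up dates reduces the bias but does not remove it. For *q* of 1% or more, the maximum among included events stops at the cut-off (365 or 455 days).

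Both illustrations pool all events, so they speak to the *All* row. Within a single preferred term the ongoing share could be lower or much higher.

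**5. Does the ongoing count repair this?** It discloses the censoring but leaves the mean, SD and maximum as they were. It is not required by product, System Organ Class (SOC) or preferred term, nor with time observed. It covers events ongoing at study end, so an event whose stop date is simply unknown is not clearly counted. Protocol 8.4.3 also allows a chronic/stable outcome, and follow-up under 8.4.6 may end there, so an event can finish follow-up with no stop date.

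**The case against.** The strongest case against is that the censoring is visible. The SAP commits to a count, and the note under Table 9-7 puts the ongoing events beneath the table. If the event number in Table 9-7 counts only events with a duration, a reader could subtract it from the event number in Table 9-6 and see the shortfall for each product and preferred term. Persistent lumps would not vanish from the report. This stands as far as it goes. The subtraction mixes ongoing events with unknown stop dates, gives no time observed, and leaves the headline statistics unlabelled.

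The SAP also uses the statistics that Protocol 10.5 prescribes, and the median, which is among them, is robust here. That stands, and it is a reason to keep those statistics and label them.

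Readers might infer three stronger things that the documents do not support:
- *The longest events are certain to be dropped and duration certain to be understated.* This depends on related events being unresolved. With no ongoing events there is no bias, and some excluded events may be short ones that began late.
- *Ongoing events disappear from the report.* The count and the table note say otherwise.
- *The SAP discards the post-study follow-up.* It is silent on those dates and does not exclude them.

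Finally, censoring every event without a stop date at last contact would be wrong. A recovered event with an unknown date ended before that contact.

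**Conclusion.** The concern holds in a limited form. If any related TEAEs are unresolved, the mean, SD and maximum in Table 9-7 describe resolved events only and can understate duration. The planned count and listing disclose the problem but do not correct it.

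The size cannot be known from the documents. On the assumptions above it runs from nil or negligible (5.50 against 5.51 days) to about a third of the mean when 10% of events are prolonged. The median shifts by at most one day. Severity is minor: safety is summarised descriptively without testing, and the primary non-inferiority conclusion does not depend on it.

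**What to change.** In SAP 2.5.2 and Table 9-7:

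1. State that stop dates from the post-study AE follow-up module (Protocol 8.4.6) are used when available.
2. Treat events with an ongoing, chronic/stable or not-recovered outcome as right-censored at last contact. Report a Kaplan-Meier median and quartiles per product for the *All* row and for preferred terms with enough events. Show the maximum as *more than x days* when the longest observed time is censored.
3. Count recovered events with an unknown stop date separately, and do not censor them at last contact.
4. Keep the protocol-specified mean, SD and maximum, labelled *events with a stop date only*. Beside them show the ongoing count and time observed by product, SOC and preferred term.

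The cost is a few sentences in the SAP and one changed table program. The downside is that Kaplan-Meier quartiles say little for preferred terms with only one or two events, which is why item 2 limits them to rows with enough events.
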